**Covariates.** Covariates will include demographic variables (age in years, education level, marital status, race/ethnicity), tobacco use and cessation history (e.g., average number of cigarettes smoked per day, severity of nicotine dependence, readiness to quit smoking), SHS exposure (smokers in the home), psychosocial measures (depression, anxiety, stress), use of other prescription medications (number), substance use severity (as measured by composite scores in the ASI-Lite), number of recent days of illicit substance use (using ASI for alcohol and other illicit drug use specifically illicit opioids, cocaine, marijuana/THC, benzodiazepines, and methamphetamine), and urine drug test results (positive/negative for marijuana, non-prescribed opioids, benzodiazepines, cocaine, methamphetamine). Covariates will be measured at baseline and at each data collection time-point (with the exception of demographic variables, which are not expected to change) Given the pilot nature of this study and the number of control variables, ability to detect differences in groups may not be possible; however, these data will provide critical information about what baseline demographic, psychosocial and substance use characteristics may be most associated with outcomes.

**Aim 3 Measures:** Using methods described by Drummond and Gold we will assess the reasonableness of the B-EPIC intervention's costs in relation to clinical outcomes achieved and examine the potential for program costs to be offset by reductions in health care utilization. Three types of economic measures will be collected during

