Anxiety	Generalized Anxiety Disorder 7 (GAD-7) is a 7-item, self-reported survey for screening and severity measuring of generalized anxiety
Perceived Stress Scale (PSS)	A 4-item scale validated to assess prenatal stress
Adverse Childhood Events (ACE)	A 10-item self-report measure developed for the ACE study to identify childhood experiences of abuse and neglect.
Hurt, Insult, Threaten and Scream (HITS)	A 4-item scale providers use to assess risk for Intimate Partner Violence (IPV)
Birth and Infant Outcomes (medical record and Kentucky Medicaid Claims Data)	
Gestational Age at Birth: Preterm Birth	Age in weeks on delivery day, and based on first trimester or earliest ultrasound (ACOG). Preterm birth defined as gestational age < 37 weeks.
Birth Weight: Low Birth Weight	First infant weight on day of delivery (grams). Low birth weight defined as < 2500 grams on day of delivery.
Neonatal Abstinence Syndrome	19-item scoring system for NAS, modified Finnegan Scale.
Well-child and Sick Visits, Hospital Admission-Readmission, Length of Stay	The International Statistical Classification of Diseases and Related Health Problems (usually abbreviated as ICD) is a diagnostic code such as 388.30 for tinnitus, unspecified.
Biological Abstinent Measures	
Urine Cotinine	Cotinine <100 ng/mL will confirm abstinence for active tobacco use
Urine Screen for Drugs of Abuse	Negative urine screen for illicit substances (iCup). If positive for anything other than buprenorphine, then quantitative laboratory analysis.

\*Age, Race/Ethnicity/Income/Education/Partner Status will also be measured

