### Statistical Analysis Plan

One hundred pregnant women undergoing medically-assisted treatment (MAT) with buprenorphine for opioid dependence will be recruited and randomized to B-EPIC ( $n=50$ ) or TAU ( $n=50$ ).

**Data Analysis (to determine the impact of the B-EPIC intervention on smoking indicators as well as birth and infant outcomes; Aims 1-2).** Data analyses will be done using SAS 9.4, with an alpha level of .05; analyses for these two aims will be done by [name]. Descriptive analysis, including means and standard deviations or frequency distributions, will be used to summarize all study variables. Baseline comparisons of covariates between the intervention group and the control, and between those who complete the study and those who drop out will be done using t-sample t-tests, Mann-Whitney U tests, or chi-square tests of association. Primary outcomes to be compared between treatment groups will include tobacco indicators, such as smoking and illicit drug use status (abstinence via urine cotinine, iCup results), smoking frequency and readiness to quit (cigarettes per day and stages of change), and maternal-child measures (gestational age of birth, birthweight, NAS, NAS severity, early childhood respiratory and ear infections). The collected variables will include not only these primary outcomes and covariates, but also feasibility indicators, such as average number of sessions completed and ratings of intervention by participants randomized to the intervention group. We will also make group comparisons between other variables that may affect maternal-child outcomes, including SHS exposure, infant feeding status at discharge (breastfeeding vs. formula), and number of people in the home. Those factors with group differences (including demographic factors measured at baseline) will be used as covariates in the corresponding analysis of group comparisons of maternal-child outcomes over time. The primary analysis strategy for the first

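### The covariate rule for maternal-child outcomes admits infant feeding at discharge, which is measured after randomisation, and adjusting for it can bias the intention-to-treat effect

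*Combined protocol and SAP*

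**What the plan says.** The Statistical Analysis Plan (Data Analysis, Aims 1-2) states: "We will also make group comparisons between other variables that may affect maternal-child outcomes". The candidates are named in the remainder of that sentence: "including SHS exposure, infant feeding status at discharge (breastfeeding vs. formula), and number of people in the home". The next sentence gives the rule: "Those factors with group differences (including demographic factors measured at baseline) will be used as covariates". Its scope is that these factors "will be used as covariates in the corresponding analysis of group comparisons of maternal-child outcomes over time". The maternal-child outcomes are listed as "gestational age of birth, birthweight, NAS, NAS severity, early childhood respiratory and ear infections". The model description that follows adds covariates to the group-by-time models to deal with group differences.

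Other sections bear on the rule:

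- **Timing of randomisation.** Women enter at under 32 weeks' gestation and are randomised once consent and screening are complete (Inclusion criteria; Randomization).
- **Estimand.** Handling Missing Data adopts intention to treat. Power Considerations puts the main emphasis on estimating effect sizes for later, larger studies.
- **SHS.** Measures (Covariates) defines the covariate as "SHS exposure (smokers in the home") and has covariates other than demographics measured at baseline and again at every time-point. The CTTS Training text makes avoidance of SHS part of B-EPIC.
- **Household size.** Number of people in the home is in neither the Covariates list nor Table 4, which has number of smokers in the home.

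**The concern.** A covariate measured after randomisation may itself be changed by assignment. Adjusting for it then removes part of the effect, or conditions on a consequence of the outcome, and the estimate is no longer the total effect of assignment. Randomisation has already removed systematic confounding, so adjusting for feeding corrects no systematic error.

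Selecting by observed difference makes this worse. The more assignment changes a factor, the more often the rule adjusts that change away. No section limits adjustment to pre-randomisation values or plans an unadjusted analysis as a check. What is at stake is the quantity the pilot is meant to hand on: effect sizes for planning a larger trial.

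**Working it through.** **1. Is feeding always post-randomisation?** Yes. Randomisation takes place in pregnancy, and discharge status exists only after birth. The parenthesis about demographic factors in the rule adds baseline factors; it does not confine the rule to them.

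**2. What role can feeding play?** Table 4 records birthweight as "First infant weight on day of delivery (grams") and gestational age on delivery day. Feeding at discharge comes later, so for these two outcomes it is a consequence or a bystander. For NAS, NAS severity and infections it may be a consequence or a mediator.

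**3. How sensitive is the screen?** The plan's own figures for covariate comparisons reproduce, at 50 per group and two-sided alpha .05:

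- t-test at 0.6 SD: noncentrality 0.6 × √(50/2) = 3.0 on 98 df, power 84.4% (plan: at least 84%).
- Chi-square, 60% against 30%: 86.6% uncorrected and 81.5% with continuity correction (plan: at least 81%).

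By the normal approximation, a continuous factor that assignment shifts by 0.3, 0.4, 0.5 or 0.6 SD is flagged with probability 32%, 52%, 71% or 85%.

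**4. How large is the bias?** The rule was simulated with 40,000 trials per scenario: ANCOVA on the factor if it differs at p<.05, otherwise unadjusted. Loss = 1 − (mean estimate under the rule ÷ true total effect). Sample sizes follow Table 2 (45 and 28 per arm). Every effect below is an assumption.

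*Feeding as a consequence of birthweight or gestational age* (true effect 0.5 SD, 45 per arm, 40% breastfed in control):

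| OR for feeding per SD of outcome | Selected | Mean estimate | Mean loss | Adjusted mean when selected |
|---|---|---|---|---|
| 1.5 | 7% | 0.496 | 1 − 0.496/0.5 = 1% | 0.486 |
| 2 | 11% | 0.484 | 3% | 0.453 |
| 3 | 17% | 0.461 | 8% | 0.407 |

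*Feeding as a mediator* (direct effect 0.3 SD; breastfeeding worth 0.2 or 0.4 SD; control 40%). True total = 0.3 + slope × rise in the breastfed proportion:

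| B-EPIC breastfed | Total (slope 0.2 / 0.4) | Selected, 45 / 28 per arm | Loss at 45 (slope 0.2 / 0.4) | Loss at 28 (slope 0.2 / 0.4) |
|---|---|---|---|---|
| 50% | 0.32 / 0.34 | 15% / 11% | 2.0% / 5.0% | 2.0% / 3.7% |
| 60% | 0.34 / 0.38 | 46% / 31% | 7.7% / 14.2% | 6.2% / 11.5% |
| 70% | 0.36 / 0.42 | 82% / 61% | 15.5% / 25.9% | 12.7% / 21.8% |

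For scale, always adjusting would lose the whole mediated part, at most 0.12/0.42 = 29%.

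**5. Follow-up SHS, if that value were used.** With a direct effect of 0.3, slope 0.2 and a shift of 0.1 or 0.2 SD, the totals are 0.32 and 0.34. At 50 per arm the rule averages 0.314 and 0.325, a loss of about 2% to 5%. At 28 per arm it averages 0.315 and 0.327, about 2% to 4%. With baseline SHS, selection occurs in 5% of trials by chance and there is no mean loss.

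**6. Against sampling error.** The SD of one trial's estimate is about √(2/45) = 0.21 at 45 per arm and √(2/28) = 0.27 at 28. The largest feeding loss is 0.259 × 0.42 = 0.11, about half of 0.21.

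**The case against.** **The plan may intend baseline screening.** It provides for "Baseline comparisons of covariates between the intervention group and the control", sets alpha at .05, names the tests, and in Power Considerations frames the covariate comparisons as baseline ones. This largely stands for SHS and household size, and it supplies an implied .05 trigger, though nothing ties that trigger to the rule. It cannot rescue feeding, which has no baseline value.

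**Feeding might never enter the birthweight model.** The rule speaks of factors that may affect outcomes and of the corresponding analysis, which could be read as leaving feeding out where the outcome came first. That reading is possible but unstated. Even without it the loss there is small: with a continuity-corrected chi-square, selection falls to about 4%, 7% and 12%, and mean loss to at most about 6%.

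**The illustration is not the planned model.** It uses a single-time ANCOVA on a continuous outcome, whereas preterm birth and NAS are to be analysed by GEE. This stands: the percentages do not carry over directly to odds ratios.

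**Two stronger readings are tempting.** A reader might infer that adjustment for SHS would remove a large share of the effect. Losses of 9% to 47% at 50 per arm do appear if SHS shifts by 0.3 to 0.7 SD with slopes of 0.2 to 0.4. Such shifts suit the 12-item exposure scale in Table 4 better, and no section names that scale as the covariate; Measures specifies smokers in the home. A reader might also infer that the rule creates false effects. With a factor shifted by 0.5 to 0.6 SD and an assumed unmeasured common cause (loading 0.5), a null effect does move by 0.11 to 0.14 SD, but the documents support neither assumption.

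**Conclusion.** The concern holds for infant feeding at discharge. The rule as written makes a post-randomisation variable eligible as a covariate in treatment-effect models, and this can bias the intention-to-treat effect. The direction and size depend on paths that the documents do not give. In the scenarios tried, where the paths run the same way, the effect is understated by about 1% to 8% on average if feeding is a consequence and about 2% to 26% if it is a mediator. If feeding is a mere bystander, there is no systematic loss. The bias is usually modest and within one trial's sampling error, but a confidence interval does not reflect it and it would carry into the planning of the next trial.

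For SHS exposure and household size the point is one of clarification: the documents lean towards baseline values, but the rule does not say so. If follow-up smokers in the home were used, the assumed shifts cost about 2% to 5%. This should be fixed, but it is not a fatal flaw in an exploratory pilot.

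**What to change.** In the Statistical Analysis Plan:

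1. Remove infant feeding at discharge from the covariate candidates.
2. State that SHS exposure means the baseline, pre-randomisation number of smokers in the home, as Measures defines it. Do the same for number of people in the home if it is collected at baseline; the documents do not show that it is.
3. State that no variable measured after randomisation enters a treatment-effect model.
4. Preferably, replace selection by observed group difference with a short baseline set named in advance, including the age randomisation stratum (30 and over against under 30).
5. Report feeding and follow-up SHS by arm descriptively, or in analyses labelled as mediation or sensitivity.

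The change is to wording and alters no sample size or power figure. Its cost is that chance baseline imbalances outside the named set are then handled only in a sensitivity analysis.

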**Power Considerations.** With approximately 50 per group and an alpha level of .05, the power of the two-sample t-test to detect a baseline group difference in a continuous covariate will be at least 84% if the ratio of the difference in means to the standard deviation is at least 0.6. This is slightly larger than a medium effect size. With approximately 50 per group and a .05 level of significance, the power of the chi-square test of association to detect an odds ratio as small as 3.5 will be at least 81%. One way to obtain an odds ratio of this magnitude would be if the prevalence of a given binary covariate at baseline were 60% in one group and 30% in the other. With at least 30 mother/baby dyads completing the study per group and an alpha level of .05, the power of the repeated measures analysis of variance F test to detect a significant main for group will be 79%, assuming a medium effect size, while the power of the F tests to detect a significant main effect of time or group by time interaction will be at least 95%, under these conditions. In the context of repeated measures modeling, a medium effect size is one such that the ratio of the standard deviation of the group means to the standard deviation of the observations within the populations is at least 0.25. Even if this ratio is smaller than a medium

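### Adjustment covariates are chosen by observed group differences, so chance decides the model, and variables measured after randomisation can enter it; a short prespecified baseline set is better.

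*Combined protocol and SAP*

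**What the plan says.** The Data Analysis paragraph for Aims 1–2 plans significance tests for "Baseline comparisons of covariates between the intervention group and the control", using t-tests, Mann-Whitney tests or chi-square tests. It then adds group comparisons of other variables that might influence maternal-child outcomes: secondhand smoke (SHS) exposure, infant feeding at discharge and household size. The selection rule follows: "Those factors with group differences (including demographic factors measured at baseline) will be used as covariates" in the matching analyses of maternal-child outcomes over time. The description of the mixed and GEE models then says, for each model, that covariates are added to control for group differences.

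No threshold for a difference is given beyond the general statement "Data analyses will be done using SAS 9.4, with an alpha level of .05". No covariate is named as a fixed model term, not even age (30 and over against under 30), which stratifies the randomisation. The Covariates paragraph under Measures gives a long list, measured at baseline and, demographics apart, at every later time-point. The plan does not say which measurement would enter a model.

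Power Considerations also sizes the baseline tests: "the power of the two-sample t-test to detect a baseline group difference in a continuous covariate will be at least 84" per cent for a difference of 0.6 SD, and "the power of the chi-square test of association to detect an odds ratio as small as 3.5 will be at least 81" per cent, with 60% against 30% as the example.

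**The concern.** Allocation is random and 1:1, so a baseline difference between arms carries no information beyond chance. Selecting on it means that a strong predictor which happens to be balanced is left out, and an irrelevant variable which happens to be unbalanced is put in. The models cannot be known until the data are seen. Age is nearly balanced by the stratification, so it would seldom be picked.

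A second problem is that not every candidate is a baseline variable. Feeding at discharge is determined after randomisation, as is SHS exposure if the follow-up values are used. The intervention could change both; the protocol says it encourages avoiding secondhand smoke and a smoke-free home. Adjusting for them can remove part of the effect or introduce bias. For gestational age and birthweight, feeding at discharge is recorded after the outcome itself.

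The stake is the precision and interpretability of the effect estimates, which the plan names as its main emphasis and wants for sizing a larger trial.

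**Working it through.** **1. The plan's own figures.** Inputs: 50 per arm ("randomized to B-EPIC ( $n=50$ ) or TAU ( $n=50"), alpha .05, taken as two-sided.

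- t-test at 0.6 SD: noncentrality 0.6 × √(50/2) = 3.0 on 98 df gives 84.4%. The plan's 84% reproduces.
- Chi-square: 60% against 30% gives odds ratio (0.6/0.4)/(0.3/0.7) = 3.5. Power = Φ{[(p₂ − p₁ − c)√50 − 1.96√(2p̄(1 − p̄))] / √(p₁(1 − p₁) + p₂(1 − p₂))}, with c = 0, or c = 1/50 for the continuity correction.
  - 30% against 60%, c = 0: (2.121 − 1.379)/0.671 = 1.107, or 86.6%. With c = 0.02: (1.980 − 1.379)/0.671 = 0.896, or 81.5%. The 81% reproduces here.
  - 10% against 28%, also odds ratio 3.5: (1.273 − 1.087)/0.540 gives 63%; with correction (1.131 − 1.087)/0.540 gives 53%. The floor of 81% therefore does not hold for odds ratio 3.5 in general.

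**2. Number of candidates.** The documents give no number; these are my counts.

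- Narrow reading: SHS exposure, feeding and household size, plus 4 demographic variables = 7.
- Broad reading, from the Covariates paragraph and the ASI-Lite entry in Table 4: demographic 4, tobacco 3, SHS 1, psychosocial 3, medications 1, ASI-Lite composites 7, use-day items 6, urine results 5 = 30. With 2 composites and 5 use-day items it is 24.

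**3. Chance selections.** Assuming independent tests at .05 and no true differences, the expected number is 0.05K and P(at least one) = 1 − 0.95^K.

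| K | Expected | P(at least one) |
|---|---|---|
| 7 | 0.35 | 30% |
| 24 | 1.2 | 71% |
| 30 | 1.5 | 79% |

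**4. Effect on power.** I simulated a linear-model test of the group effect, which with complete data equals the between-subject test on subject means. Three analyses were compared: unadjusted; adjusted for every covariate with baseline p < .05; adjusted for three prespecified covariates. The correlation between covariates (rho) and the share of outcome variance explained (R²) are assumptions, because the documents give neither. The table uses 30 candidates, 20,000 trials per row and effects set for about 80% unadjusted power. The 30-per-arm size comes from the plan's longitudinal power ("With at least 30 mother/baby dyads completing the study per group"). Cells show none / rule / prespecified, in %.

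| R² | rho | 50 per arm | 30 per arm |
|---|---|---|---|
| 0 | 0 | 80.1 / 76.8 / 78.8 | 78.6 / 72.7 / 76.5 |
| 0.1 | 0.15 | 79.6 / 77.3 / 82.6 | 78.5 / 73.7 / 80.6 |
| 0.3 | 0 | 79.6 / 77.4 / 90.6 | 78.9 / 74.2 / 89.4 |
| 0.3 | 0.3 | 80.0 / 80.5 / 90.8 | 78.6 / 77.4 / 89.0 |
| 0.5 | 0.3 | 80.0 / 81.7 / 97.3 | 78.2 / 78.6 / 96.5 |

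The rule against no adjustment runs from −5.9 to +1.7 points. The −5.9 arises when screening and analysis use the same 30 per arm; screening all 50 and analysing 30 gives −4.0 (78.5% to 74.5%).

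A second set used an effect of 0.5 SD and uncorrelated covariates. With R² 0.25, power is 70 / 68 / 81% for 100 women and 44 / 40 / 54% for 56 women (the Table 2 completers). With R² 0.35 and 56 women it is 45 / 40 / 59%. With only 7 candidates and R² 0.25, none against rule is 68.5% against 68.9% (rho 0) and 70.2% against 71.1% (rho 0.3): no loss.

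Type I error under the rule was about 3.6–5.5%.

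**The case against.** The best defence is that the rule does less harm than it seems. Several parts of that stand.

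- A reader might infer that the rule always has less power than no adjustment. The documents do not support this. The sign depends on a correlation they do not give, and many of the listed measures overlap (depression, anxiety and stress; drug-use severity, days of use and urine results). At rho 0.3 the loss vanishes or reverses at 50 per arm.
- A reader might take 30 screening tests as the plan's figure. The sentence stating the rule follows a short list and refers to maternal-child outcomes. The later model description extends adjustment to every model but names no list. Both readings are open. The .05 cut-off is likewise inferred from the general alpha.
- A large gain from prespecification requires covariates that are prognostic. At R² 0 the prespecified set is 2 to 4 points above the rule but 1 to 2 points below no adjustment. With R² 0.3 spread evenly over 30 uncorrelated variables, any three give 80.2% against 78.6% for the rule.
- Time-constant covariates entered as main effects leave the group-by-time test essentially unchanged with complete data.
- The 56-women and 30-per-arm figures treat completers as the analysed sample, whereas the plan keeps drop-outs in the models.
- The Covariates paragraph already concedes that the number of control variables may prevent detection of differences, and the trial is a pilot.

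None of this defends selection by imbalance. The pilot purpose points the other way: with 56 women and R² 0.25, the SD of the estimated effect is about 0.27–0.29 under the rule and 0.24 with prespecified covariates. Nor does it answer the post-randomisation candidate, which is named in the narrow list itself.

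**Conclusion.** The point holds. The plan selects covariates by group difference, fixes none in advance, and lets at least one post-randomisation variable into the comparison. The possible bias from that variable cannot be sized from the documents.

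For group main effects and single-time outcomes such as birthweight, with rho 0 to 0.3, the rule lies between about 6 points below and 2 points above no adjustment. Prespecified covariates beat it by about 3–7 points at R² 0.10 and about 9–20 points at 25–35%, with little or no benefit if they are not prognostic. These figures rest on assumed correlations and R², on p < .05 as the screen, and on continuous outcomes; the binary GEE models were not simulated.

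A reader might also infer a false-positive problem; the simulations show none. The 84% is correct and the 81% is correct for its example. Both describe baseline tests and say nothing about power for the outcomes.

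**What to change.** Before outcomes are compared by arm:

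1. Delete the group-difference rule from the Data Analysis paragraph and the matching clause in the model description.
2. Name a fixed set for each outcome family: the age stratum; the baseline value of the outcome where one exists, either as a covariate or as the first time-point of the repeated-measures model, not both; and two or three prognostic baseline covariates already collected. Examples are nicotine dependence and smokers in the home for tobacco outcomes, and nicotine dependence and baseline substance-use severity for birth and NAS outcomes.
3. State that covariates enter at their baseline value, and that the primary comparison is not adjusted for feeding at discharge, follow-up SHS exposure or any other post-randomisation variable.
4. Keep the between-arm baseline table descriptive, without tests. The comparison of completers with drop-outs can stay.
5. In Power Considerations, restrict the 81% to 30% against 60%, or drop both baseline-test sentences.

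The cost is wording and a few degrees of freedom: one for age, two or three for the prognostic covariates, and one more if the baseline value is a covariate, so three to five per model. No new data are needed. For rare binary outcomes such as cessation the set should stay at the short end.

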**Table 4: Summary of Outcomes Measures (SOMs)**

Variable (Name)	Measure
Susceptibility to use	Items adapted from 4 item questionnaire for susceptibility to initiate smoking.
Switching/dual use	A series of yes/no items to discern dual use and switching behavior.
Fagerstrom Test for Nicotine (Cigarette) Dependence	The Fagerstrom Test for Nicotine Dependence (FTND) is a 6-item scale that measures dependence on nicotine.
Electronic Cigarette Dependence Index	The Electronic Cigarette Dependence Index is a 10-item scale that measures dependence to electronic cigarettes.
Perceptions of conventional tobacco and e-cig use	
Proportion of women/ pregnant or postpartum women using e-cigs	Item adapted from questionnaire used to examine normative perceptions of smoking among teen girls. (Example: 'How many women/pregnant or postpartum women do you think use e-cigs?')
SHS and e-cigarette vapor exposure	
Home, Family & Peer Tobacco Use	Home SHS exposure will be assessed by number of smokers in home. To assess their family members' and peers' tobacco (and e-cig) use, the participants will be asked to identify (from a list provided) which individuals in their lives use tobacco.
Exposure to SHS smoke and e-cig vapor	12-item scale on exposure to SHS to assess environmental impact. We will adapt this scale to apply to e-cig vapor.
Other substance use	
Substance Use Severity and recent (Last 30 days use) from Addiction Severity Index (ASI)-Lite	Composite scores of drug and alcohol use severity and five other domains of function that are affected by substance use: medical, family, social, legal, and employment problem severity are collected. Also, number of days of drug use in the last 30 days will be assessed for all major classes of substances (e.g., alcohol, cocaine, benzodiazepines...).
Psychosocial, Lifestyle and Safety Measures	
Stages of Change	The short form for the Classification of Stages of Change for Smoking Cessation is a 3 item assessment to indicate.

Variable (Name)	Measure
Readiness to Quit (smoking cessation)	A “ladder scale” with 10 options to indicate an individual’s readiness to quit tobacco use
Edinburgh Postnatal Depression Scale (EPDS)	A 10-item scale examines clinical depressive symptoms in pregnant and postpartum women. Higher scores indicate more depressive symptoms. Tool has been consistently validated in pregnant and postpartum women.

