two study aims will be two-factor (group x time) repeated measures mixed models; these will be estimated using the MIXED procedure or group comparisons of continuous outcomes over time, including cigarette use and tobacco dependence. Generalized estimating equation (GEE), analyses with an exchangeable correlation structure will be used to assess for significant differences between groups and across time for categorical and dichotomous outcomes (e.g., preterm birth, NAS) using the SAS GENMOD procedure. The main effects of group and time and the interaction between them will be included in each model, and covariates will be added to control for group differences. As appropriate, post-hoc pairwise comparisons will be done using Fisher's least significant difference procedure for mixed models and using contrast statements for GEE models.

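### Cigarettes per day and other repeated continuous outcomes: baseline appears to be modelled as a fourth response, so the group main effect captures only three quarters of a constant later difference, and baseline adjustment is not secured

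*Combined protocol and SAP*

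**What the plan says.** The Statistical Analysis Plan (Data Analysis, Aims 1-2) uses group-by-time mixed models for "group comparisons of continuous outcomes over time, including cigarette use and tobacco dependence". On the model terms it says: "The main effects of group and time and the interaction between them will be included in each model". The primary outcomes include "smoking frequency and readiness to quit (cigarettes per day and stages of change"; Table 4 also lists a 10-step ladder, "Readiness to Quit (smoking cessation)".

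The survey and urine collection take place four times, and Table 3 labels the first occasion as baseline. Power Considerations describes the repeated comparison as covering 4 time-points. It gives separate power for the group main effect (79% at f = 0.25, 60% at f = 0.20) and for the time or interaction effect (at least 95%, and 87%). It does not say which term is the treatment test. Pairwise comparisons are available, but only post hoc.

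Three statements bear on covariates:

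- The Covariates paragraph under Measures lists "average number of cigarettes smoked per day, severity of nicotine dependence, readiness to quit smoking" and adds "Covariates will be measured at baseline and at each data collection time-point".
- The Data Analysis paragraph says "Those factors with group differences (including demographic factors measured at baseline) will be used as covariates", in a sentence about maternal-child outcomes.
- The sentence that lists the model terms ends "covariates will be added to control for group differences".

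Randomisation is stratified by age at 30 years. Age stratum is not named as a model term.

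**The concern.** None of the three covariate statements secures the baseline value of the outcome being modelled. The first covers values at every visit, and adjusting follow-up cigarettes per day for follow-up cigarettes per day would condition on the outcome itself. The other two tie adjustment to group differences.

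If baseline is a free response, the group main effect averages a visit at which no effect can be expected with three at which one can. Power Considerations says the main purpose of the group comparisons is to estimate effect sizes for planning a larger trial, but not which estimate will be used. If it is the four-visit group effect, the next trial would be planned on a diluted value. The interaction is not diluted in this way, but it does not use the fact that randomised arms are equal at baseline by design, and so it loses power.

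The scope is limited to continuous outcomes measured at baseline and again later: mainly cigarettes per day, also dependence and the readiness ladder if it is analysed. Birth and NAS outcomes are measured once and are unaffected. The SD figures do not apply to stage of change if it is analysed by GEE. Cotinine abstinence gains little, because all participants smoke at entry.

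**Working it through.** **Inputs.** Power Considerations gives alpha 0.05, 30 completers per arm (N = 60), 4 time-points, and f = 0.25 or 0.20. Table 2 gives retention of 50, 45, 39 and 28 per arm. The documents give no within-woman correlation ρ.

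**1. The plan's own power.** With m = 4 visits, the noncentrality is f²Nm/[1+(m−1)ρ] for group (1, 58 df) and f²Nm/(1−ρ) for interaction (3, 174 df). Solving for ρ gives about 0.3.

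| Term | f | Noncentrality | Power | Stated |
|---|---|---|---|---|
| Group | 0.25 | 0.0625×240/1.9 = 7.89 | 78.9% | 79% |
| Group | 0.20 | 0.04×240/1.9 = 5.05 | 59.9% | at least 60% |
| Interaction | 0.25 | 0.0625×240/0.7 = 21.4 | 98.0% | at least 95% |
| Interaction | 0.20 | 0.04×240/0.7 = 13.7 | 88.2% | 87% |

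The stated power is right for its own f. With m = 3, no single ρ tried between 0 and 0.6 fits all four figures, which supports reading baseline as a response.

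**2. The 0.75 factor.** For differences (0, d, d, d) the equally weighted group effect is 3d/4 = 0.75d, whatever ρ is. With two arms, f is half the standardised difference, so f = 0.375d and f = 0.25 means d = 0.25/0.375 = 0.67 SD. At d = 0.5, f = 0.1875, the noncentrality is 0.1875²×240/1.9 = 4.44, and power with 30 completers per arm is 54.5%.

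**3. All available data under Table 2.** Table 2 implies these dropout patterns per arm: 5 women with visit 1 only, 6 with visits 1-2, 11 with visits 1-3, 28 with all four. I used generalised least squares with exchangeable correlation and the same dropout in both arms. *Group* is the mean of the four differences (1, 98 df) and *interaction* has 3, 218 df. *Adjusted* constrains the arm means to be equal at baseline, and is tested as the average of the three later differences (1, 97 df) or jointly (3, 218 df).

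Power (%) at d = 0.5 SD, for ρ = 0.3 / 0.5 / 0.7:

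| Differences over the 4 visits | Group | Adjusted average | Interaction | Adjusted joint |
|---|---|---|---|---|
| 0, d, d, d | 71/61/54 | 90/93/98 | 51/66/87 | 80/84/94 |
| 0, 0, d, d | 38/32/28 | 58/62/76 | 56/71/91 | 67/77/93 |
| 0, d, 0, 0 | 13/12/11 | 19/21/26 | 49/64/87 | 56/68/88 |
| 0, d, d/2, 0 | 24/20/18 | 37/40/51 | 44/59/82 | 58/67/86 |

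Constant later difference detectable with 79% power: group 0.55/0.62/0.67 SD; interaction 0.67/0.58/0.45; adjusted joint 0.49/0.47/0.40; adjusted average 0.43/0.41/0.35.

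**4. Precision.** The standard errors in SD units are 0.1484/0.1660/0.1809 for the group effect and 0.1520/0.1455/0.1244 for the adjusted average. Multiplying the group effect by 4/3 removes the dilution but leaves (16/9)×SE²(group)/SE²(adjusted) = 1.69/2.31/3.76 times the variance.

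**5. Generality.** With equal baseline means, the constrained estimate has the smaller variance for any pattern of later effects, and the joint test uses a constraint that the interaction ignores. Over 3,000 random effect patterns, with ρ from 0.05 to 0.90, neither adjusted test fell below its counterpart.

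**6. Simulation.** Over 1,000 runs per ρ, with REML-estimated covariance and a constant 0.5 SD, power was: group 71/61/51%, average 91/93/96%, interaction 52/67/86%, joint 83/85/92%. The mean group effect was 0.37-0.38 and the mean adjusted average 0.49-0.50. Under last observation carried forward, which the plan also specifies, power was: group 60/53/41%, average 86/90/96%, interaction 48/62/82%, joint 74/79/89%. Null rejection was 3.8-5.7% for all tests. Multiple imputation was not modelled.

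**The case against.** The strongest reply is that the dilution is conditional. The plan never says that the group main effect is the treatment estimate. The interaction is in every model with its own stated power, and neither it nor the visit contrasts are shrunk. That is correct. But the plan does not choose the interaction either, and the adjusted joint test beats it in every profile. The margin can be small: at ρ = 0.7 it is 91 to 93% for a postpartum-only effect and 87 to 88% for a third-trimester-only effect.

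The Covariates list can be read as already planning adjustment, since it names tobacco history without condition and the selection rule is worded for maternal-child outcomes. This supports calling the plan ambiguous, not silent. It does not secure a baseline-only term.

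The 0.67 SD figure rests on completers, a basis the plan itself calls conservative. With all Table 2 data and ρ = 0.3 the detectable difference is 0.55 SD, and power at 0.5 SD is 71%. Larger losses depend on assumed correlations. The calculations also assume normal errors with equal SD, which is approximate for a cigarette count with zeros.

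The plan does not say whether the first survey precedes randomisation. Equal expected baseline means require that it does, so this should be confirmed before arm means are constrained equal.

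Finally, this is a pilot. Since its main product is effect sizes for a larger trial, that makes the choice of estimate matter more.

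**Conclusion.** The concern holds and should be fixed. The 0.75 factor is exact for an equally weighted four-visit group effect when the later difference is constant and the arms are equal at baseline. It matters if that effect is used as the test or carried forward. Whichever term is meant, a baseline-adjusted counterpart did at least as well in every profile checked. For a constant 0.5 SD the gain is from 71/61/54% to 90/93/98% over the group main effect, and from 51/66/87% to 80/84/94% over the interaction.

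The power figures rest on assumed exchangeable correlations of 0.3 to 0.7, Table 2 retention with equal dropout by arm, and a baseline measured before allocation. That baseline is a response is inferred from the count of four time-points and the Table 3 label. The issue is efficiency and the effect size reported, not false-positive risk.

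**What to change.** For continuous outcomes measured at baseline and follow-up:

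- Model the three post-baseline visits, with the outcome's baseline value and the age stratum as prespecified covariates whether or not the arms differ. Keeping baseline as a response with arm means constrained equal is an alternative, once it is confirmed that the first survey precedes randomisation.
- Do not use the four-visit group main effect as the treatment effect, or as the effect size for the next trial.
- Report baseline-adjusted B-EPIC minus TAU differences with confidence intervals at each later visit and as their average.
- Name the lead test in advance. The average is stronger for a lasting effect, and the joint 3-df test for one that is delayed or fades. The choice is the sponsor's.
- Restate power as a post-baseline difference in SD units, with the assumed correlation and Table 2 retention.

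The cost is SAP wording. Baseline values and age stratum are already collected, and no visit, measurement or participant is added. The only trade-off is which of the two adjusted tests leads.
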